7.2 Subject Population(s) for Analysis

All-Treated Population: The analysis will be performed on all corticosteroid non-responders subsequently treated with 84 consecutive days of anakinra. The primary analysis will consist of determining whether an improvement in either audiometric threshold or speech discrimination can be achieved with anakinra in patients that did not respond to corticosteroids. The secondary analysis will be to determine whether anakinra can be administered safely for an 84 consecutive day period without significant complications in this patient population.

8 Safety and Adverse Events

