4.4 Early Withdrawal of Subjects

4.4.1 When and How to Withdraw Subjects

Some patients may be prematurely withdrawn prior to completion of the drug for several reasons. Indications for early termination of anakinra administration is (1) Development of neutropenia as defined as an ANC of <1000, (2) Development of a serious bacterial infection (pneumonia, cellulitis, septicemia) (3) Severe injection site reaction, (4) Rash consistent with an allergic reaction to Anakinra, (5) Significant worsening of hearing threshold in either ear (greater than 20dB worsening of the pure tone average) (6) Development of renal insufficiency (as determined by a creatinine clearance of <49mL/min). The patient may also self-withdraw due to intolerance of daily injections. Although abrupt termination of drug should not pose a safety issue, a greater concern exists for hearing deterioration. If this occurs, prednisone therapy will immediately be reinstituted, barring any patient contraindications to continued corticosteroid therapy. If anakinra therapy is terminated due to safety concerns, corticosteroid therapy may be recommended, only if further hearing deterioration occurs off anakinra. Also see section 9.5: Stopping Rules. If a patient is withdrawn during study treatment, a follow-up audiogram, all safety bloods and IL-1 levels will be done approximately within 30 days of the last injection.

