4.4.2 Data Collection and Follow-up for Withdrawn Subjects

Even if patients prematurely withdraw, or are withdrawn from the study, an analysis of all data collected through the time of withdrawal will be included for analysis. Data on the withdrawn

CONFIDENTIAL This material is the property of the Feinstein Institute for Medical Research, North-Shore-LIJ Health System. Do not disclose or use except as authorized in writing by the study sponsor subjects is critical to the integrity of the final data analysis, especially for safety and tolerability issues.

5 Study Drug

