5.5 Subject Compliance Monitoring

Patients will be given a 28 day supply of medication, record keeping materials and a sharps container. The patient will be asked to send an email (at least weekly) to the study nurse indicating the time of injection and any noted skin or other reactions while on study drug. If the study nurse has not been contacted by the enrolled subject in a 7 day period, the nurse will contact the patient by telephone to check their status. If the patient will be without email access for a given period, this information will be conveyed to the nurse prior to the period, and the patient will fill out a written log book during this period. In the event the patient does not have email access, the patient will fill out a log book daily. The study nurse will contact these patients weekly (by phone) to check their status. It is anticipated that the majority of subjects will communicate by email. Compliance will also be monitored by having the patient return the sharps container monthly. Although spent needles will not be pulled out and counted, the

volume of needles in the container can be estimated. In the event a patient is non-compliant, the patient will be contacted by the physician that enrolled the patient. The physician will determine the cause of non-compliance. For any patient that has a greater than 72 hour lapse in treatment not dictated by a physician, in most cases, these subjects will be informed that they will be withdrawn from the study.

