7.1 Sample Size Determination & Statistical Methods

Corticosteroid resistant AIED patients currently have no therapeutic alternatives available to them. These patients that failed initial corticosteroid therapy are not expected to demonstrate a placebo effect, as they have already undergone 2 serial audiograms that demonstrated a <5dB PTA improvement in hearing for trial inclusion. A Simon 2-stage "optimal" design will be used to test the null hypothesis that the true objective response rate (RR) is 10% or less (which would not be clinically meaningful) versus the alternative hypothesis that the true response rate is 30% or greater. With a significance level of 0.05 and a power of 0.80, a maximum total of 29 evaluable patients will be required to assess the objective response rate. Ten (10) evaluable patients will be enrolled in Stage 1(R21 phase). If 1 or fewer objective responses are observed in the first 10 evaluable patients, then the trial will be terminated (do not proceed to R33). Primary milestone: If 2 or more objective responses (improvement in the PTA \geq 5dB) are observed in the first 10 patients (20%), we will proceed to the R33 phase.

If the RR is 10% or less, then the expected sample size for the trial is 15 patients and the probability of early termination at the end of the R21 phase (stage 1) is 74%. Overall, a total of approximately 38 patients may be enrolled in this R21/R33 study to ensure that the specified numbers of evaluable patients are available for analysis at each stage.

Given that anakinra may cause injection site reactions, it is possible that some patients will prematurely self-terminate the study. In order to appropriately evaluate the results, 29 patients would need to complete the 84-day course of anakinra. Overall, a total of 38 patients may be enrolled in this study to ensure that the specified numbers of evaluable patients are available for analysis at each stage.

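### The All-Treated Population in 7.2 is defined as 84-day completers, which contradicts its own label and section 4.4.2 and can take early stoppers out of the response rate

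*Protocol*

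**What the plan says.** Section 7.2 defines one analysis set and labels it All-Treated: "The analysis will be performed on all corticosteroid non-responders subsequently treated with 84 consecutive days of anakinra". It then describes the primary (hearing) and secondary (safety) analyses under that definition.

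Section 7.1 uses the same idea for the sample size: "With a significance level of 0.05 and a power of 0.80, a maximum total of 29 evaluable patients will be required", and later "In order to appropriately evaluate the results, 29 patients would need to complete the 84-day course of anakinra". Enrolment of up to 38 is allowed so that enough evaluable patients are available at each stage. The hypotheses are that "the true objective response rate (RR) is 10% or less" against the alternative that "the true response rate is 30% or greater". The text does not say whether these rates refer to treated or to evaluable patients.

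Section 4.4.2 points the other way. For patients who leave early, "an analysis of all data collected through the time of withdrawal will be included for analysis", and it calls these data critical, above all for safety and tolerability.

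Section 4.4.1 lists the reasons for ending treatment: neutropenia, serious bacterial infection, severe injection site reaction, allergic rash, renal insufficiency, and "Significant worsening of hearing threshold in either ear (greater than 20dB worsening of the pure tone average"). It also requires a follow-up audiogram and safety bloods after withdrawal. Section 5.5 adds that, after a lapse of more than 72 hours not ordered by a physician, "in most cases, these subjects will be informed that they will be withdrawn from the study".

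**The concern.** A set called All-Treated should hold everyone who was treated. This one holds only those who received 84 consecutive days. One reason for stopping, worsening of the pure tone average (PTA), is the opposite of response on the scale that defines response. A patient whose hearing falls far enough is taken off drug and then, under 7.1 and 7.2, drops out of the denominator, and the surplus enrolment supplies a replacement. In an uncontrolled trial judged on one proportion, that can raise the response rate at both the 10-patient decision and the final test.

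The protocol also gives two incompatible instructions, because 4.4.2 is not limited to safety and so conflicts with 7.2 on efficacy as well. A later analysis plan cannot follow both. Read literally, 84 consecutive days would also exclude patients with a lapse of up to 72 hours, whom 5.5 does not single out for withdrawal.

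**Working it through.** **Inputs from section 7.1.** p0 = 0.10, p1 = 0.30, significance level 0.05, power 0.80; stage 1 of 10 patients, stopping at 1 or fewer responses; maximum 29 evaluable; enrolment up to 38.

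**Reproducing the plan.** An exact binomial search for the Simon optimal design gives stage 1 boundary 1/10 and final boundary 5/29, so success needs at least 6 of 29. The protocol does not state this final cut-off; it follows from the search. With X1 ~ Bin(10, p) and X2 ~ Bin(19, p):

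- P(early stop) = P(X1 ≤ 1) = 0.736 at p = 0.10 (stated 74%)
- Expected N = 10 + (1 − 0.736) × 19 = 15.0 (stated 15)
- P(reject) = Σ over x = 2 to 10 of P(X1 = x) × P(X2 ≥ 6 − x) = 0.047 at p = 0.10 and 0.805 at p = 0.30

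The stated design is reproduced.

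**Implied withdrawal.** 38 − 29 = 9, and 9/38 = 23.7%. This is the loss that the enrolment figure allows for, not a stated withdrawal rate. The other rates below are assumptions.

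**Type I error when only completers are counted.** Take 10% as the true rate among all treated patients. If a fraction d withdraws and the leavers respond at rate s, the completer rate is q = (0.10 − d·s)/(1 − d). Putting q into the formula for P(reject):

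| d | response among leavers | q | type I error |
|---|---|---|---|
| any | same as completers (10%) | 0.100 | 0.047 |
| 10% | none | 0.111 | 0.071 |
| 20% | none | 0.125 | 0.110 |
| 9/38 | half the overall rate (5%) | 0.116 | 0.082 |
| 9/38 | none | 0.131 | 0.130 |
| 30% | none | 0.143 | 0.173 |

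In the 9/38 case with no responders among leavers, the chance of wrongly passing stage 1 rises from 1 − 0.736 = 0.264 to 1 − 0.616 = 0.384.

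**Same data, two denominators.** Six responders are 6/29 = 20.7% of completers but 6/38 = 15.8% of treated patients.

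**Power if early stoppers count as non-responders.** Suppose 30% was meant among completers and withdrawal is unrelated to response. The rate among treated patients is 0.30 × (1 − d), and the power of the 1/10, 5/29 rule is 0.720 at d = 10%, 0.610 at 20% and 0.564 at 9/38 (rate 0.30 × 29/38 = 0.229).

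**Using the 38 already planned.** Keep stage 1 and require at least 8 of 38 treated (second-stage size 28). P(reject) is 0.023 at 10% and 0.808 at 30%. Requiring 7 instead gives 0.052 at 10%, just over the limit.

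**The case against.** **Safety.** A reader might infer from 7.2 that toxicity withdrawals are removed from the safety analysis and that treatment-ending toxicity would be zero by construction. The protocol does not support that. Section 4.4.2 keeps withdrawn patients' data for safety. Section 3.3 sets safety endpoints with no completer restriction. Section 8.1 runs adverse event reporting to 30 days after the last dose. Section 8.5 has a study-level rule that counts patients prevented from completing therapy. The closing reference to the patient population in 7.2 could also mean steroid-resistant patients generally. What stands is a contradiction that needs resolving.

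**Failures in general.** A reader might infer that treatment failures leave the response rate. Only those who stop early can do so.

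**Size.** The 0.130 needs all nine surplus patients to leave and none to be a responder. Section 7.1 attributes early loss to injection site reactions, which need not relate to hearing. The stopping rule in 8.5 might also halt the study before nine withdrawals, although its n=5 does not match 25% of 38 (9.5) and it is unclear whether patients who withdraw themselves count. So 0.130 is an upper bound at 9/38, not an expected value.

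**Estimand.** If 10% and 30% were meant among evaluable completers, the error is 0.047 as designed. That is a fair reading of 7.1. It then answers a narrower question than the All-Treated label implies and still conflicts with 4.4.2.

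**Discretion over lapses.** A reader might infer that withdrawal after a lapse could be steered by a known audiogram. Section 5.5 does leave discretion in an open-label trial, but nothing links it to hearing results, and 6.1 blinds audiologists to the timepoint. This remains a possibility only.

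**Conclusion.** The point holds for efficacy as a stated rule that contradicts both its own label and section 4.4.2. Followed as written, 7.1 and 7.2 take early stoppers, including patients withdrawn for marked hearing worsening, out of the denominator that decides the stage 1 go/no-go and the final test.

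If the 10% null refers to all treated patients and withdrawal is no higher than the implied 9/38, the type I error lies between 0.047 and 0.130 when leavers respond no more often than completers. It is about 0.08 if they respond at half the overall rate. These figures also rest on the derived cut-off of 6 of 29.

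For safety, the conclusion is limited to an unresolved conflict between 7.2 and 4.4.2. It should be corrected before the analysis, because the choice of denominator can turn the same six responders from 20.7% into 15.8%.

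**What to change.** In 7.1 and 7.2, define the primary efficacy set and the safety set as all patients who received at least one dose, at stage 1 and at the final analysis. Count patients who stop early without a day-84 audiogram as non-responders. Keep the 84-day completers as a sensitivity analysis. State that 10% and 30% refer to treated patients, and write the final cut-off into 7.1. Reword 7.1, 7.2 and 4.4.2 so that they name the same sets, and say how a short lapse in dosing affects completer status.

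No new data are needed, since 4.4.1 already requires an audiogram and safety bloods after withdrawal. The cost is a less favourable response rate and a sample size decision:

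- If the rates refer to treated patients, at least 8 of the 38 already planned, with stage 1 unchanged, gives type I error 0.023 and power 0.81.
- If 30% was meant among completers, the 29-patient rule has power as low as 0.56 at 9/38 withdrawal. The protocol should say so, or the sample size should be revisited.

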3.2 Primary Study Endpoints

The primary endpoint is to determine whether those treated with anakinra for 84 days demonstrate an improved hearing threshold compared with their pre-anakinra-treatment threshold.

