4.1 Inclusion Criteria

1. Patients must have Autoimmune Inner Ear Disease, Meniere's Disease, or Sudden Sensorineural Hearing Loss with autoimmune features.

CONFIDENTIAL This material is the property of the Feinstein Institute for Medical Research, North-Shore-LIJ Health System. Do not disclose or use except as authorized in writing by the study sponsor

- 2. Age and Gender: males and females ages 13 to 75 weighing 90 lbs or greater will be recruited.
- 3. Patients must be capable of understanding and giving informed consent.
- 4. If the recruited patient is between the ages of 13 and 17, an assent will be obtained from the patient and consent from one parent/legal guardian prior to enrollment.
- 5. Patients must have SNHL of greater than 30dB at one or more frequencies in one or both ears with evidence of active deterioration (elevated threshold) in at least one ear of 15 dB at one frequency (excluding 250 or 8kHz as a sole indicator) on their audiogram, or 10dB at 2+ frequencies developing in >3 days but <90 days, or in the case of SSNHL, the hearing loss may evolve in less than 3 days if the patient displays features suggestive of an autoimmune disorder.
- 6. Patients must have previously undergone a trial of high-dose corticosteroid therapy, at 60 mg daily for a minimum of seven days, with a variable taper thereafter that consists of a total of 30 consecutive days of corticosteroid use. Patients must have demonstrated less than or equal to a 5 decibel average improvement in their PTA in response to corticosteroids as measured by their audiogram.
- 7. Patients may have a concurrent other autoimmune disease(s).

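### The primary response is a PTA gain of 5 dB or more in 7.1 but threshold or speech discrimination in 7.2, with no scored ear named, so error control at 0.05 is not assured for the 7.2 response

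*Protocol*

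**What the plan says.** Three sections of the protocol describe the primary outcome.

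- **3.2 Primary Study Endpoints**: whether patients treated for 84 days "demonstrate an improved hearing threshold compared with their pre-anakinra-treatment threshold". No size of change, ear or speech component is given.
- **7.1 Sample Size Determination & Statistical Methods**: the null is that "the true objective response rate (RR) is 10% or less (which would not be clinically meaningful". The alternative is a rate of at least 30%. The size is then given: "With a significance level of 0.05 and a power of 0.80, a maximum total of 29 evaluable patients will be required". The go/no-go rule defines the response: "Primary milestone: If 2 or more objective responses (improvement in the PTA". The gain it asks for is 5 dB or more, counted over the 10 stage 1 patients.
- **7.2 Subject Population(s) for Analysis**: "The primary analysis will consist of determining whether an improvement in either audiometric threshold or speech discrimination can be achieved with anakinra". No cut-off is given for either measure.

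On the ear, 3.1 requires loss in both ears for the first 10 subjects, and 4.1 (criterion 5) requires loss "with evidence of active deterioration (elevated threshold) in at least one ear". Section 4.4.1 refers to either ear, but only for withdrawal after worsening. No section names the ear scored for response.

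The only speech cut-off, a gain of more than 12%, is in 3.1. It belongs to the definition of response to prednisone, not to anakinra.

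**The concern.** A patient whose PTA does not improve but whose speech discrimination does is a non-responder under 7.1 and a responder under 7.2. A statistical analysis plan could add detail, but it could not follow both sections.

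The hypotheses belong to the PTA response. Section 7.1 argues that no placebo effect is expected because two earlier audiograms showed a PTA gain below 5 dB, and inclusion criterion 6 also screens on PTA alone. Neither says how often speech discrimination would improve by chance. A second route to response can only raise the chance rate, and nothing in the protocol supports 10% as the null for the wider response.

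The trial is single-arm and open-label, and one responder count decides its result. If the measure, the size of change or the ear is settled after data are seen, the choice can change the conclusion.

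**Working it through.** **Inputs from 7.1.** Null 0.10, alternative 0.30, alpha 0.05, power 0.80, 10 patients in stage 1 (stop at 1 or fewer responses), maximum 29. The final cut-off is not stated. A search for the optimal design with these inputs gives 1/10 and 5/29, that is, success at 6 or more of 29.

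**Reproducing the plan's figures.** For response rate p:

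- Early termination: (1−p)^10 + 10p(1−p)^9. At p = 0.10 this is 0.3487 + 0.3874 = 0.736 (stated: 74%).
- Expected N: 10 + 19 × (1 − 0.736) = 15.0 (stated: 15).
- Rejection: Σ over x = 2 to 10 of P[Bin(10,p) = x] × P[Bin(19,p) ≥ 6−x]. This is 0.047 at p = 0.10 and 0.805 at p = 0.30.

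The design is sound for one fixed response. It has little slack: the error passes 0.05 once the true null rate exceeds about 10.15%.

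**Assumptions, none given in the protocol.** The PTA null rate is a = 0.10 in one ear. The speech chance rate is s = 0.05 or 0.10. The two responses arise from correlated normal variables cut at those rates (latent correlation).

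**Composite rate.** u = a + s − P(both). If independent, 0.10 + 0.05 − 0.005 = 0.145, and 0.10 + 0.10 − 0.01 = 0.190.

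**Speech route, with stage 1 on PTA as 7.1 states.** Only the final count uses the composite. With x PTA responders and y speech-only responders in stage 1:

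Σ over x = 2 to 10 of P[Bin(10,a) = x] × Σ over y of P[Bin(10−x, (u−a)/(1−a)) = y] × P[Bin(19,u) ≥ 6−x−y]

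This cannot exceed the chance of passing stage 1 on PTA, 1 − 0.736 = 0.264.

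**Ear route.** If either ear counts at both stages at 10% per ear, the rejection formula applies with p = u.

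| Case | Latent correlation | Composite rate | Error, ≥6/29 | Error, ≥9/29 |
|---|---|---|---|---|
| One fixed PTA response | – | 0.100 | 0.047 | 0.001 |
| PTA 10%, speech 5% | 0.5 | 0.131 | 0.097 | 0.007 |
| PTA 10%, speech 5% | 0 | 0.145 | 0.122 | 0.013 |
| PTA 10%, speech 10% | 0.7 | 0.153 | 0.135 | 0.018 |
| PTA 10%, speech 10% | 0 | 0.190 | 0.189 | 0.047 |
| Either ear, 10% each | 0.7 | 0.153 | 0.215 | 0.024 |
| Either ear, 10% each | 0 | 0.190 | 0.384 | 0.078 |

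The last column reads the synopsis's 30% as an observed rate: 0.30 × 29 = 8.7, so 9 or more.

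**Low-rate case.** Two independent components at 5% each give u = 0.05 + 0.05 − 0.0025 = 0.0975. The error is then 0.043 at 6 or more of 29, even with the composite used at both stages.

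**The case against.** The strongest reply is that loss of error control is not shown. Section 7.1 presents 10% as the limit below which a response rate has no clinical value, not as an estimate of chance response. If chance rates are low, even the wider response stays under 0.05. This stands: a reader might infer that the 10% null and the 0.05 level fail, but the protocol gives no component rates from which to prove it.

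A reader might also infer that the speech route loosens the go/no-go decision and pushes the error to 0.28 to 0.38. It does not. The milestone is written on PTA, so for that step only the ear is open, and the speech route is capped at 0.264.

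Nor does the protocol say that a gain in either ear counts. It is silent on the ear, and an analysis plan may settle that. The per-ear figures show what the silence would permit, not a written rule.

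The figures also depend on the missing final cut-off. At 9 or more of 29, nearly all cases stay below 0.05. That reading fits poorly with 7.1, however, because power at 30% would be 0.497 rather than the stated 0.80. The synopsis may simply be restating the alternative.

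Finally, the either/or response may be the intended one. Exclusion 15 treats word recognition as essential to judging efficacy, and 3.1 defines steroid response by PTA or speech. This stands and bears on the fix. Section 3.2 can be read as a general statement that 7.1 makes operational, so the real conflict is between 7.1 and 7.2.

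**Conclusion.** The point holds as a contradiction in the definition of the primary response, with the scored ear unspecified. Control at 0.05 is not assured for the 7.2 response; it is not shown to be lost.

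With a 10% PTA null rate and the 1/10, 5/29 rule, the illustrative type I error is about 0.10 to 0.12 (speech chance rate 5%) or 0.14 to 0.19 (10%). It is 0.21 to 0.38 if either ear were allowed to count at both stages. These ranges rest on assumed chance rates, assumed correlations and a final cut-off that the protocol does not state. The conflict between 7.1 and 7.2 needs no assumption and should be corrected.

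**What to change.** State one primary response, in the same words, in 3.2, 7.1 and 7.2. Give the measure, the size of change, the comparison (day 84 against the time 0 audiogram) and the scored ear. Name the ear before the first dose, by the deterioration that qualified the patient, with a stated rule for when both ears qualify. State the final cut-off alongside. Then choose one of two options.

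1. **PTA improvement of 5 dB or more in the scored ear**, with speech discrimination and the fellow ear secondary. The design and N = 29 stand, and no new measurement is needed. The cost is that fewer patients are labelled responders.
2. **The either/or response**, if that is the intention. Give cut-offs for both measures, justify a null rate for the composite, apply the same definition at both stages and restate the Simon figures. The cost is a changed design. Keeping the 20-point difference, a null of 15% against 35% gives 1/9 and 8/34, and 19% against 39% gives 3/14 and 11/39. These nulls are illustrative. The second needs more evaluable patients (39) than the 38 planned for enrolment.
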